6.2.1 Evaluations for Follow Up

- Patients will be seen in follow-up 30 days post treatment then at 8-12 weeks post-treatment and every 8-12 weeks for 24 months with the following evaluations:
- Complete physical evaluation with a performance status, vital signs, height, and weight, and a complete medical history
- Dose Limiting Toxicity Assessment
- MRI scans at 8-12 weeks post-treatment and every 8-12 weeks for 24 months for assessment of response to therapy and monitoring.
- Administration of Fact-Brain questionnaire 30 days post treatment, 8 -12 weeks post treatment, and at time of each follow-up visit/scan.

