6.4.1.2 Definition of local control

In this study, patients will be recorded as having a lesion that is locally controlled if they have stable disease (SD), partial response (PR), or complete response (CR) in the target lesion; all of which are defined above. Patients will be recorded as having local failure if they have progressive disease (PD) within the target lesion. Patients that develop new lesions outside the target volume will be coded as having a regional intracranial failure. A distant failure will be defined as new brain metastases outside of the treatment volume.

6.4.1.3

HRQL studies (Fact-Brain) will be completed prior to treatment, and following treatment to coincide with follow-up exams and MRI scans. See appendix III for a full version of the Fact-Brain questionnaire.

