7.0 Statistical Considerations

7.1 Definitions

Primary Objective

To determine the maximum tolerated dose (MTD) and safety of fractionated SRS when treating brain metastases

- Primary Endpoint: Maximum Tolerated Dose: the maximum amount of Gy fractionated stereotactic radiosurgery (FSRS) delivered without significant toxicity

Secondary Objectives

To evaluate the local control associated with this therapy.

To evaluate regional intracranial failure associated with this therapy.

To evaluate the Health Related Quality of Life (HRQL) associated with this therapy.

Secondary Endpoints

- Local control: proportion of patients with Complete Response (CR), Partial Response (PR), or Stable Disease (SD) in the target lesion
- Regional intracranial failure: proportion of patients that develop new lesions outside the target volume
- Health Related Quality of Life (HRQL) measured by Functional Assessment of Cancer Therapy – General (FACT-Brain) assessment.

The following definitions will be useful in explaining the trial design.

7.1.1 *Toxicity*

In this section, *toxicity* is taken to mean unacceptable, dose-limiting toxicity, as defined in Section 5.2.4, as any adverse event that occurs between the first fraction of radiotherapy and 60 days after the last fraction of radiotherapy. The primary goal of the TITE-CRM design employed in this trial is to identify the radiation dose associated with toxicity in 1/6=16.7% of patients (the MTD); this is referred to as the *target rate*.

7.1.3 *Expected rates of toxicity*

Based on previous treatment experience, the *expected rates of toxicity* have been estimated (Table 7.1). These rates will be re-evaluated throughout the trial as treatment experience is accrued in accordance with the TITE-CRM algorithm.

Radiation Dose	Expected Probability of Acute Toxicity
24 Gy	0.08
27 Gy	0.11
30 Gy	0.14
33 Gy	0.17
36 Gy	0.20

Table 7.1. Expected probabilities of toxicity

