7.3.2 Analysis of Secondary Endpoints

2. The proportion patients experiencing local control at each dose will be calculated with 95% exact confidence intervals. The dose-response function, describing the probability of local control at each dose, will be estimated using logistic regression, along with likelihood ratio profile confidence intervals.
3. The probability of failure will be analyzed in a similar fashion to the probability of intracranial failure.
4. The analysis of HRQL data (Section 6.5.1.4) will be descriptive. The data will be summarized by question at each time point with the frequency and percentage of each quality level. For each patient, the trajectory of the score will be plotted against time.

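### HRQL is described only by item frequencies per visit and individual plots of an undefined score, so no group-level change from baseline is quantified

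*Combined protocol and SAP*

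**What the plan says.** Sections 2.0 and 7.1 give the objective as "To evaluate the Health Related Quality of Life (HRQL) associated with this therapy". The endpoint is "Health Related Quality of Life (HRQL) measured by Functional Assessment of Cancer Therapy – General (FACT-Brain) assessment". Neither section names a score, a time point, a hypothesis or a threshold.

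On timing, the text under Section 6.4.1.3 says "HRQL studies (Fact-Brain) will be completed prior to treatment, and following treatment to coincide with follow-up exams and MRI scans". Sections 6.1 and 6.1.1 confirm the pre-study form. Section 6.2.1 adds forms at 30 days, at 8-12 weeks and at each later visit, with follow-up running to 24 months.

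The analysis is item 4 of Section 7.3.2, which has three sentences. The first labels the HRQL work as descriptive and points to another section for the data. The second sets out the only output that groups patients together: "The data will be summarized by question at each time point with the frequency and percentage of each quality level". The third turns to individual patients and plans a plot of each one's score over time.

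The section cited in the first sentence does not appear in the text. HRQL is dealt with in 6.4.1.3, which defines no score either.

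**The concern.** The objective concerns HRQL in relation to the treatment, and a pre-treatment form is collected that could serve as the reference. Yet the only output that summarises patients together is a set of response distributions, one per question per visit. Each distribution comes from whoever is present at that visit.

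Two things follow. The tables do not link a patient's answer at one visit to the same patient's answer at another. And the patients behind later tables are likely to differ from those behind earlier ones. Section 4.3 requires a life expectancy of only 12 weeks, while HRQL follow-up lasts 24 months. Section 8.1.1 lists progression, serious illness and dose-limiting toxicity as reasons for removal, and the documents do not say whether forms continue after removal. A reader who compares the visit tables could take the departure of sicker patients for improvement.

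The trajectory plots do link visits within a patient, but they show a score that the plan never defines.

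**Working it through.** The plan states no precision, power or sample size for HRQL, so there is no figure to reproduce. Four checks bear on the point.

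**1. Do item frequencies identify change?** Take one item and 25 patients (the maximum in Section 7.4), with 12 at one level and 13 at the next level up at baseline, and the same 12 and 13 at a later visit. The counts fit nobody having changed. They also fit all 12 moving up while 12 of the 13 move down: 12 patients are then at the lower level, 12 + 1 = 13 are at the upper level, and 24 of 25 have changed. Identical tables thus allow anything from 0 to 24 changers.

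**2. Can the tables move when nobody changes?** Keep the same baseline, with the upper level the better one: 13/25 = 52% are at the better level. Assume 10 patients are lost, leaving 15, and that no remaining patient changes. The documents give no HRQL dropout figure, so both the number lost and the pattern of loss are assumptions.

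| Assumed losses (worse level + better level) | Remaining at better level |
|---|---|
| 5 + 5 | 8/15 = 53% |
| 10 + 0 | 13/15 = 87% |

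The apparent shift runs from almost none to 35 percentage points (87 − 52), depending only on who leaves. The second row is an extreme, not a forecast.

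**3. Is the plotted score defined?** Appendix III uses one 0-4 scale for items of opposite direction. A high answer on lack of energy is unfavourable; a high answer on enjoying life is favourable. The emotional domain holds both kinds. A score therefore needs a reversal rule and a choice of total or subscale. Sections 2.0, 6.4.1.3, 7.1 and 7.3.2 give neither.

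**4. What would a paired estimate deliver?** The documents give no SD for the score, so the result is in units of the SD of the individual changes. For a mean change, the 95% half-width is t(0.975, n−1)/√n. The values of n below 25 are assumed.

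| Pairs n | Half-width (SD of change) |
|---|---|
| 25 | 0.41 |
| 20 | 0.47 |
| 15 | 0.55 |
| 10 | 0.72 |
| 5 | 1.24 |

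At 15 to 25 pairs the interval is wide but readable. At 5, which is an even split of 25 over the five dose levels, it is not, so the estimate should pool dose levels.

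**The case against.** The strongest reply is that the plan already suits its purpose. This is a dose-finding trial of at most 25 evaluable patients, the HRQL objective is only to evaluate, and the analysis is openly labelled descriptive. Because a form is completed before treatment, the trajectory plots can start at baseline and show change within each patient. A reader might infer that the HRQL objective cannot be answered at all. The documents do not support that: up to 25 individual plots, together with the item tables, do describe HRQL over time. What the reply leaves standing is that the plots show change only by eye, for an unspecified score, and give no group estimate.

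A second reply is that pairing does not cure attrition. That is correct. A paired change at a visit still uses only patients who survived and completed the form. Pairing ensures that the same people stand on both sides of the comparison, which reduces the problem without removing it. It is also true that item frequencies already show how many patients answered at each visit, so the number alive is the main addition to the counts.

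A third reply concerns the instrument's name. A reader might infer from "measured by Functional Assessment of Cancer Therapy – General (FACT-Brain) assessment" and from the four general domains in Appendix III that the brain-specific items were left out. That does not follow. Sections 6.1, 6.1.1, 6.2.1 and 6.4.1.3 consistently refer to FACT-Brain, and the appendix may be incomplete in the text available. The label is a minor wording correction.

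**Conclusion.** The point holds as a minor weakness in the choice of summary. Item 4 of Section 7.3.2 quantifies no group-level change in HRQL from baseline, its tables cannot identify change within patients, and the score to be plotted is undefined. Comparing the visit tables also mixes change with selective loss. How much cannot be said, because the documents give no HRQL dropout figure.

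The conclusion does not depend on any assumed SD, correlation or attrition rate. Only the illustration of shifting tables and the precision figures below n = 25 use assumed numbers. The primary objective and the dose decision are unaffected.

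**What to change.** Amend item 4 of Section 7.3.2 as follows:

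- Define the FACT-Brain total and subscale scores, including which items are reversed.
- Report the mean or median paired change from baseline with a 95% confidence interval at 30 days and at 8-12 weeks, pooled over dose levels. Leave later visits descriptive.
- Give the number alive and the number completing the form at each visit.
- State that the paired estimates apply to patients who were alive and completed the form.
- Keep the trajectory plots and item tables as supporting output.
- Label the analysis as descriptive and added after dose escalation, since Sections 3.3 and 5.2.3 report the MTD as already determined.

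Correct the cross-reference in item 4, and use one name for the instrument in Sections 2.0 and 7.1 and Appendix III.

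The change needs no new patients, visits or forms. Its costs are modest precision (half-width about 0.41 SD of change at best for a mean), remaining selection by survival, and a late addition that must be declared as such.

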8.0 Data Safety and Recording

8.1 Data and safety monitoring plan

All patient data will be collected by the Clinical Research Department of Radiation Oncology. All data will be secured in a password protected file with observance of all applicable HIPAA regulation. A data safety monitoring board will meet monthly to evaluate toxicity for this trial. Patients/adverse events will be discussed at the Radiation Oncology Data Safety meetings. Unexpected serious adverse events will be reported to the IRB and DSMC, and minutes of the monthly disease center meetings will be reviewed at the DSMC meetings. Reports will be submitted annually at the time of the yearly renewal.

8.1.1 Subject Removal Criteria

1. Disease progression
2. Development of a serious medical illness
3. Evidence of dose-limiting toxicity
4. Voluntary withdrawal
5. Severe Protocol Non Compliance
6. Discretion of the principal investigator
7. Development of grade 4 toxicity related to experimental therapeutic
8. Pregnancy

8.2 Safety Reporting

8.2.1 Acute Adverse Events

The CTCAE (described below) will be used to grade acute toxicity during this trial.

CTCAE term (AE description) and grade: The descriptions and grading scales found in the revised NCI Common Terminology Criteria for Adverse Events (CTCAE) version 4.0 will be utilized for AE reporting. All appropriate treatment areas will have access to a copy of the CTCAE version 4.0. A copy of the CTCAE version 4.0 can be downloaded from the CTEP web site (<http://ctep.cancer.gov>).

An AE is any untoward medical occurrence in a patient or clinical investigation subject administered a pharmaceutical product that does not necessarily have a causal relationship with this treatment. An AE can therefore be any unfavorable and unintended sign (including an abnormal laboratory finding), symptom, or disease temporally associated with the use of a medicinal (investigational) product, whether or not related to the medicinal (investigational) product.

It may include worsening or increase in severity of signs or symptoms of the illness, increase in frequency of signs and symptoms of an intermittent illness, or the appearance of a new manifestation/complication.

Exacerbation of a pre-existing illness should be considered when a subject requires new or additional concomitant drug or non-drug therapy for the treatment of that illness during the study. Lack of or insufficient clinical response, benefit, efficacy, or therapeutic effect should not be recorded as an adverse event. The investigator must make the distinction between exacerbation of pre-existing illness and lack of therapeutic efficacy.

In addition, abnormal objective test findings (e.g., electrocardiogram changes, abnormal laboratory test results) that can result in a change in study drug dosage or in discontinuation of the drug, or require intervention or diagnostic evaluation to assess the risk to the patient, should also be recorded as adverse events. Clinically significant changes in physical examination findings should also be recorded as adverse events. For all adverse events, the investigator must pursue and obtain information adequate both to determine the outcome of the adverse event and to assess whether it meets the criteria for classification as a serious adverse event requiring immediate notification to the IRB or its designated representative.

All observed or volunteered adverse events regardless of treatment group or suspected causal relationship to study drug will be recorded on the adverse event page(s) of the CRF. The investigator will record all adverse events in the CRF and assess each event as to severity and causal relationship to study drug.

‘Expectedness’: AEs can be ‘Unexpected’ or ‘Expected’ for expedited reporting purposes only.

Attribution of the AE:

Definite – The AE is *clearly related* to the study treatment.
Probable – The AE is *likely related* to the study treatment.
Possible – The AE *may be related* to the study treatment.
Unlikely – The AE is *doubtfully related* to the study treatment.
Unrelated – The AE is *clearly NOT related* to the study treatment.

For all adverse events, sufficient information should be obtained by the investigator to determine the causality, (i.e., study drug or other illness). The investigator is required to assess causality and indicate that assessment on the CRF. Follow-up of the adverse event, after the date of therapy discontinuation, is required if the adverse event or its sequelae persist. Follow-up is required until the event or its sequelae resolve or stabilize at a level acceptable to the investigator. Adverse events that continue, or emerge within 30 days, after the patient’s discontinuation or completion of the study will be followed until the events resolve, are considered stable, or can be ascribed to causes other than study treatment.

All serious AE shall be reported meeting criteria for reporting can be found on the University of Pittsburgh Institutional Review Board’s website at <http://www.irb.pitt.edu>. In the event of such adverse event, the investigator must report the event(s) via phone within 24 hours and a written report filed within 24 hours to the Principal Investigator.,

References:

References:

2. Patchell R. Brain metastases. *Handbook of neurology.* 25: 135, 1997

Appendix I

Response Evaluation Criteria in Solid Tumors (RECIST) Quick Reference:

Eligibility

- Only patients with measurable disease at baseline should be included in protocols where objective tumor response is the primary endpoint.

Measurable disease - the presence of at least one measurable lesion. If the measurable disease is restricted to a solitary lesion, its neoplastic nature should be confirmed by cytology/histology.

Measurable lesions - lesions that can be accurately measured in at least one dimension with longest diameter ≥ 20 mm using conventional techniques or ≥ 10 mm with spiral CT scan.

Non-measurable lesions - all other lesions, including small lesions (longest diameter <20 mm with conventional techniques or <10 mm with spiral CT scan), i.e., bone lesions, leptomeningeal disease, ascites, pleural/pericardial effusion, inflammatory breast disease, lymphangitis cutis/pulmonis, cystic lesions, and also abdominal masses that are not confirmed and followed by imaging techniques; and.

- All measurements should be taken and recorded in metric notation, using a ruler or calipers. All baseline evaluations should be performed as closely as possible to the beginning of treatment and never more than 4 weeks before the beginning of the treatment.
- The same method of assessment and the same technique should be used to characterize each identified and reported lesion at baseline and during follow-up.
- Clinical lesions will only be considered measurable when they are superficial (e.g., skin nodules and palpable lymph nodes). For the case of skin lesions, documentation by color photography, including a ruler to estimate the size of the lesion, is recommended.

Methods of Measurement –

- CT and MRI are the best currently available and reproducible methods to measure target lesions selected for response assessment. Conventional CT and MRI should be performed with cuts of 10 mm or less in slice thickness contiguously. Spiral CT should be performed using a 5 mm contiguous reconstruction algorithm. This applies to tumors of the chest, abdomen and pelvis. Head and neck tumors and those of extremities usually require specific protocols.
- Lesions on chest X-ray are acceptable as measurable lesions when they are clearly defined and surrounded by aerated lung. However, CT is preferable.
- When the primary endpoint of the study is objective response evaluation, ultrasound (US) should not be used to measure tumor lesions. It is, however, a possible alternative to clinical measurements of superficial palpable lymph nodes, subcutaneous lesions and thyroid nodules. US might also be useful to confirm the complete disappearance of superficial lesions usually assessed by clinical examination.
- The utilization of endoscopy and laparoscopy for objective tumor evaluation has not yet been fully and widely validated. Their uses in this specific context require sophisticated equipment and a high level of expertise that may only be available in some centers. Therefore, the utilization of such techniques for objective tumor response should be restricted to validation purposes in specialized centers. However, such techniques can be useful in confirming complete pathological response when biopsies are obtained.
- Tumor markers alone cannot be used to assess response. If markers are initially above the upper normal limit, they must normalize for a patient to be considered in complete clinical response when all lesions have disappeared.

- Cytology and histology can be used to differentiate between PR and CR in rare cases (e.g., after treatment to differentiate between residual benign lesions and residual malignant lesions in tumor types such as germ cell tumors).

Baseline documentation of “Target” and “Non-Target” lesions

- All measurable lesions up to a maximum of five lesions per organ and 10 lesions in total, representative of all involved organs should be identified as ***target lesions*** and recorded and measured at baseline.
- Target lesions should be selected on the basis of their size (lesions with the longest diameter) and their suitability for accurate repeated measurements (either by imaging techniques or clinically).
- A sum of the longest diameter (LD) for *all target lesions* will be calculated and reported as the baseline sum LD. The baseline sum LD will be used as reference by which to characterize the objective tumor.
- All other lesions (or sites of disease) should be identified as ***non-target lesions*** and should also be recorded at baseline. Measurements of these lesions are not required, but the presence or absence of each should be noted throughout follow-up.

Response Criteria

Evaluation of target lesions

- * Complete Response (CR): Disappearance of all target lesions
- * Partial Response (PR): At least a 30% decrease in the sum of the LD of target lesions, taking as reference the baseline sum LD
- * Progressive Disease (PD): At least a 20% increase in the sum of the LD of target lesions, taking as reference the smallest sum LD recorded since the treatment started or the appearance of one or more new lesions
- * Stable Disease (SD): Neither sufficient shrinkage to qualify for PR nor sufficient increase to qualify for PD, taking as reference the smallest sum LD since the treatment started

Evaluation of non-target lesions

- * Complete Response (CR): Disappearance of all non-target lesions and normalization of tumor marker level
- * Incomplete Response/ Stable Disease (SD): Persistence of one or more non-target lesion(s) or/and maintenance of tumor marker level above the normal limits
- * Progressive Disease (PD): Appearance of one or more new lesions and/or unequivocal progression of existing non-target lesions (1)
 - (1) Although a clear progression of “non target” lesions only is exceptional, in such circumstances, the opinion of the treating physician should prevail and the progression status should be confirmed later on by the review panel (or study chair).

Evaluation of best overall response

The best overall response is the best response recorded from the start of the treatment until disease progression/recurrence (taking as reference for PD the smallest measurements recorded since the treatment started). In general, the patient's best response assignment will depend on the achievement of both measurement and confirmation criteria

Target lesions	Non-Target lesions	New Lesions	Overall response
CR	CR	No	CR
CR	Incomplete response/SD	No	PR
PR	Non-PD	No	PR
SD	Non-PD	No	SD
PD	Any	Yes or No	PD
Any	PD	Yes or No	PD
Any	Any	Yes	PD

- Patients with a global deterioration of health status requiring discontinuation of treatment without objective evidence of disease progression at that time should be classified as having “symptomatic deterioration”. Every effort should be made to document the objective progression even after discontinuation of treatment.
- In some circumstances it may be difficult to distinguish residual disease from normal tissue. When the evaluation of complete response depends on this determination, it is recommended that the residual lesion be investigated (fine needle aspirate/biopsy) to confirm the complete response status.

Confirmation

- The main goal of confirmation of objective response is to avoid overestimating the response rate observed. In cases where confirmation of response is not feasible, it should be made clear when reporting the outcome of such studies that the responses are not confirmed.
- To be assigned a status of PR or CR, changes in tumor measurements must be confirmed by repeat assessments that should be performed no less than 4 weeks after the criteria for response are first met. Longer intervals as determined by the study protocol may also be appropriate.
- In the case of SD, follow-up measurements must have met the SD criteria at least once after study entry at a minimum interval (in general, not less than 6-8 weeks) that is defined in the study protocol

Duration of overall response

- The duration of overall response is measured from the time measurement criteria are met for CR or PR (whichever status is recorded first) until the first date that recurrence or PD is objectively documented, taking as reference for PD the smallest measurements recorded since the treatment started.

Duration of stable disease

- SD is measured from the start of the treatment until the criteria for disease progression are met, taking as reference the smallest measurements recorded since the treatment started.
- The clinical relevance of the duration of SD varies for different tumor types and grades. Therefore, it is highly recommended that the protocol specify the minimal time interval required between two measurements for determination of SD. This time interval should take into account the expected clinical benefit that such a status may bring to the population under study.

Response review

- For trials where the response rate is the primary endpoint it is strongly recommended that all responses be reviewed by an expert(s) independent of the study at the study's completion. Simultaneous review of the patients' files and radiological images is the best approach.

Reporting of results

- All patients included in the study must be assessed for response to treatment, even if there are major protocol treatment deviations or if they are ineligible. Each patient will be assigned one of the following categories: 1) complete response, 2) partial response, 3) stable disease, 4) progressive disease, 5) early death from malignant disease, 6) early death from toxicity, 7) early death because of other cause, or 9) unknown (not assessable, insufficient data).
- All of the patients who met the eligibility criteria should be included in the main analysis of the response rate. Patients in response categories 4-9 should be considered as failing to respond to treatment (disease progression). Thus, an incorrect treatment schedule or drug administration does not result in exclusion from the analysis of the response rate. Precise definitions for categories 4-9 will be protocol specific.
- All conclusions should be based on all eligible patients.
- Subanalyses may then be performed on the basis of a subset of patients, excluding those for whom major protocol deviations have been identified (e.g., early death due to other reasons, early discontinuation of treatment, major protocol violations, etc.). However, these subanalyses may not serve as the basis for drawing conclusions concerning treatment efficacy, and the reasons for excluding patients from the analysis should be clearly reported.
- The 95% confidence intervals should be provided.

